### **Sample Size Calculations**

The original trial of the U@Uni intervention achieved an initial response rate of 31.34% to the recruitment emails and was able to obtain at least one follow-up data point from 76.60% of respondents. Assuming the same response and retention rates for the repeat trial, this would produce a total sample size of  $5000 \times .3134 \times .7660 = 1200$  (i.e., 600 per arm of the trial). This sample will be sufficient to detect a standardised effect size of  $d = 0.20$  at a two sided significance level of .0127 (the p value has been adjusted to allow for multiplicity in the co-primary endpoints) with 80% power. Webb et al. [13] reported that the overall effect size of internet-based health behaviour interventions was  $d = 0.16$ , although this increased for interventions based on the TPB ( $d = 0.36$ ) and those using implementation intentions ( $d = 0.25$ ). Given that the proposed intervention incorporates these additional features, we anticipate sufficient power to detect differences between the intervention and control arms in outcomes. For the hair analysis, a sample size of 100 participants will be sufficient to detect a medium effect size of  $d=0.40$  ( $\alpha=.05$ ,  $\text{power}=.80$ ).

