### **Principal Research Questions**

The primary research question is whether, compared to a measurement only control arm, an online digital intervention (“U@Uni LifeGuide”) delivered during the transition from school to university produces significant changes in the health behaviours (i.e., fruit and vegetable intake, physical activity, alcohol consumption, smoking) of young people six months after starting university. Additional research questions that will be addressed include whether the intervention: (i) changes health beliefs (and whether these changes mediate the effect of the intervention on the health behaviours), (ii) enhances health status, (iii) reduces health service usage, (iv) reduces recreational drug use, and (v) reduces BMI.

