### **Analyses**

Both the data and the health economic analyses will follow the same procedure as outlined in the study protocol paper for the original U@Uni trial [14] and reported in the accompanying papers [1, 5]. Thus, multivariate analysis will be conducted to assess the impact of the intervention on each of the four targeted health behaviours at six-month follow-up, controlling for age, gender, nationality and baseline scores.

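### The sample size counts anyone with any follow-up (76.60%), but the primary outcome is at six months, so 1200 is an upper bound and the 80% power is not yet supported

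*Protocol*

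**What the plan says.** The Sample Size Calculations section of the Protocol takes two rates from the original trial. For response, that trial "achieved an initial response rate of 31.34% to the recruitment emails". For retention, the section uses the fact that the same trial "was able to obtain at least one follow-up data point from 76.60% of respondents". It carries both rates forward ("Assuming the same response and retention rates for the repeat trial") and multiplies them by the number invited: "5000 \times .3134 \times .7660 = 1200". Split evenly, this is given as "i.e., 600 per arm of the trial". The section calls this number sufficient for d = 0.20 with 80% power "at a two sided significance level of .0127", a level adjusted for the co-primary endpoints.

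The Recruitment, Randomization and Allocation section and Table 1 set two follow-ups, at one and six months, and all four primary outcomes are collected at both. The Principal Research Questions section places the primary question on the behaviours "of young people six months after starting university". The Analyses section says that the analysis will "assess the impact of the intervention on each of the four targeted health behaviours at six-month follow-up", adjusting for age, gender, nationality and baseline scores. For the rest of the procedure it refers to the original trial's published protocol and results. The Protocol does not state the original trial's six-month completion rate.

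**The concern.** The retention rate in a sample size calculation should describe the people who will have the outcome being powered. Here it describes people with either of two follow-ups, while the outcome being powered is measured at the second. Anyone who answered at one month and not at six is counted as analysable without having a six-month value. The 76.60% equals six-month completion only if nobody in the original trial fell into that group.

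The stated power applies to all four co-primary endpoints. The Background reports that the original trial found no significant effect on three of its four primary outcomes, and that the repeat trial is meant to give more precise estimates. Readers of a second null result will look at what effect the trial could have detected, and that figure currently rests on the most favourable possible value for six-month completion.

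**Working it through.** **Inputs from the Protocol (Sample Size Calculations):** 5000 invited; response .3134; any-follow-up rate .7660; d = 0.20 (so SD = 1); two-sided alpha .0127; power 80%; equal arms.

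**Assumed, because the Protocol does not give them:** the six-month completion rate (50% to 76.6% of respondents) and the correlation r between baseline and six-month scores (0.3 and 0.5).

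**Step 1: reproduce the plan's figures.**
- Respondents: 5000 × .3134 = 1567.
- Times .7660: 1200.3, or 600 per arm. This matches.
- Alpha: a Sidak adjustment for four endpoints gives 1 − 0.95^(1/4) = .01274. This matches .0127.
- Number needed per arm, normal approximation: n = 2(z₁ + z₂)²/d², with z₁ = 2.492 for alpha and z₂ = 0.842 for power. This is 2 × 11.11/0.04 = 556. The t-test version gives about 557.
- Power with 600 per arm (t-test): 83.3%.

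So 1200 is enough for 80% power if all 1200 have six-month data.

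**Step 2: find the break-even completion rate.** 2 × 557.2/1567 = 71.1%. The margin is 76.6 − 71.1 = 5.5 percentage points. Unadjusted power is below 80% if more than about that share of respondents have one-month data only.

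**Step 3: vary six-month completion.** Analysable number per arm = 1567 × rate/2. Two-sample t-test, no covariate adjustment:

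| Assumed six-month completion | Per arm | Power at d = 0.20 | d detectable with 80% power |
|---|---|---|---|
| 76.6% (upper bound) | 600 | 83.3% | 0.193 |
| 70% | 548 | 79% | 0.202 |
| 65% | 509 | 76% | 0.209 |
| 60% | 470 | 72% | 0.218 |
| 50% | 392 | 62% | 0.239 |

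**Step 4: allow for the planned baseline adjustment.** For a continuous outcome, adjusting for baseline multiplies the residual variance by 1 − r².
- r = 0.5 (factor 0.75): power is about 85% at 60% completion, 81% at 55% and 77% at 50%. The number needed is about 557 × 0.75 = 418 per arm, and break-even is 2 × 418/1567 = 53%.
- r = 0.3 (factor 0.91): power is about 80% at 65% completion and 76% at 60%. The number needed is about 557 × 0.91 = 507 per arm, and break-even is 2 × 507/1567 = 65%.

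This applies to fruit and vegetable intake, physical activity and alcohol units. It does not carry over directly to smoking status, which is categorical.

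**The case against.** The strongest reply is that nothing stated has been shown to be false. The section says 1200 is sufficient, and 600 per arm in fact gives 83.3%. That leaves room for some loss, and at 70% completion unadjusted power is still 79%. The planned analysis also adjusts for baseline, which the calculation ignores, so for three of the four outcomes the unadjusted figures are pessimistic. With r = 0.5 the trial keeps 80% power down to about 53% completion. All of this stands, and it limits how serious the point is.

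A second reply is that the Analyses section defers to the original trial's procedure, which is not at hand. A repeated-measures or imputation analysis could let students with only one-month data enter. This stands in part. A reader might infer that such students contribute nothing to the primary comparison, but the Protocol does not say so. Even so, a one-month value would normally recover only part of the information in a six-month value, so counting these students as full six-month observations would still need a justification that the section does not give.

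A reader might also infer that the trial is underpowered. The documents do not support that: no six-month rate is given, and any rate of about 71% or more leaves the stated power intact even without adjustment.

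Nor is this a matter to leave to a statistical analysis plan. The Protocol makes the calculation itself and chooses the input.

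**Conclusion.** The concern holds as a fault in a sample size input. The retention rate used is an upper bound on the rate that matters for the six-month outcome, so 1200 (600 per arm) is an upper bound on the number of students with that outcome. The multiplication, the adjusted alpha and the power at 600 per arm are all correct, so this is not an arithmetic error.

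How far power falls cannot be settled from the Protocol. It depends on the original trial's six-month completion rate, on the baseline correlation for the continuous outcomes, and on whether one-month data are used for missing six-month values. Over the assumed range of 70% down to 50%, unadjusted power runs from 79% to 62%, and moderate baseline correlations recover much of the loss for the continuous outcomes. A shortfall is possible but not demonstrated. The point should be fixed; it does not call the design into question.

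**What to change.** In the Sample Size Calculations section, replace 76.60% with the original trial's six-month completion rate, which the investigators should hold because that trial reported six-month results. Then restate the analysable number per arm, the power at d = 0.20 and two-sided .0127, and the d detectable with 80% power.

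If credit is taken for baseline adjustment, state the assumed correlation for each continuous outcome and treat smoking status separately. If credit is taken for one-month data, name the method that uses them.

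Recruitment, endpoints, alpha and analysis need not change. The cost is one revised paragraph, and the stated power or detectable effect may become slightly less favourable.

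### The only multiplicity rule stated is a single level of .0127; if it also serves as the decision rule for all four endpoints, its step-down version would be more powerful at the same 5% family-wise error

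*Protocol*

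**What the plan says.** Under Principal Research Questions, the protocol asks whether the intervention "produces significant changes in the health behaviours" and lists four: "fruit and vegetable intake, physical activity, alcohol consumption, smoking". Under Analyses it plans to "assess the impact of the intervention on each of the four targeted health behaviours at six-month follow-up", adjusting for age, gender, nationality and baseline scores. That section gives no significance level, ordering or stopping rule, and takes its procedure from the published protocol and papers of the original trial.

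Multiplicity appears once, under Sample Size Calculations. The trial is powered "at a two sided significance level of .0127 (the p value has been adjusted to allow for multiplicity in the co-primary endpoints"). The expected analysed sample is 1200 ("i.e., 600 per arm of the trial"), stated to be enough for d = 0.20 with 80% power. Neither the adjustment method nor the family-wise level is named.

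**The concern.** A single-step rule holds each endpoint to the same strict level whatever the other three show. A step-down rule starts at that level and relaxes it after each success. Both keep the chance of any false claim at or below the same limit, but the single-step rule leaves part of that allowance unused as soon as one effect is real.

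The point matters here because the intervention takes each participant through a module on every one of the four behaviours. Several real effects are what the trial hopes for, and that is where a single-step rule gives up most power. At stake is the number of behaviours on which a real effect can be claimed. The validity of the claims is not in question.

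**Working it through.** **Inputs.** From Sample Size Calculations: two-sided level .0127, d = 0.20, 600 per arm, 80% power, response 31.34%, retention 76.60%. From Principal Research Questions and Analyses: four endpoints. Assumed: 5% family-wise level, normal test statistics, equal correlation of 0, 0.2 or 0.5 between endpoints (the protocol gives none), and d = 0.20 as a common scale, which is only an approximation for binary smoking status.

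**1. The protocol's own figures.**
- Level: 1 − 0.95^(1/4) = .01274, which rounds to .0127. Bonferroni would be .05/4 = .0125. So .0127 is Sidak for four tests at 5%.
- Sample: 5000 × .3134 × .7660 = 1200.3.
- Power: Φ(d√(n/2) − z). Here 0.20 × √300 = 3.464 and z at .0127 two-sided is 2.492, so Φ(0.972) = 83.4%.
- Needed for 80%: 2 × (2.492 + 0.842)² / 0.20² = 556 per arm.

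All the stated figures hold, with a small reserve.

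**2. Step-down thresholds.** With k hypotheses still open the level is 1 − 0.95^(1/k):

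| Ordered p-value | k | Threshold | Power at d = 0.20, 600 per arm |
|---|---|---|---|
| Smallest | 4 | .0127 | 83.5% |
| Second | 3 | .0170 | 85.9% |
| Third | 2 | .0253 | 89.0% |
| Largest | 1 | .0500 | 93.4% |

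(The first row uses the unrounded .01274, hence 83.5% and not 83.4%.) No threshold is below .0127, so every p-value that passes the single-step rule also passes here.

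**3. Power under each rule, independent endpoints.** The four thresholds cut the p-value scale into five bands. The probability of each band is known for a true effect (from the table above) and for a null (from the thresholds). Summing over all 5⁴ = 625 combinations gives exact results:

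| True effects | Power per true effect, single-step | Step-down | Family-wise error, single-step | Step-down |
|---|---|---|---|---|
| 0 | – | – | 5.0% | 5.0% |
| 1 | 83.5% | 83.6% | 3.8% | 4.8% |
| 2 | 83.5% | 85.6% | 2.5% | 4.5% |
| 3 | 83.5% | 88.2% | 1.3% | 4.2% |
| 4 | 83.5% | 91.9% | – | – |

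A simulation with 500,000 replicates agrees to within 0.1 point.

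**4. Showing all four, when all four effects are d = 0.20.** For the single-step rule under independence this is 0.8348⁴ = 48.6%. The correlated rows are simulated:

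| Correlation | Single-step | Step-down | Gain (points) |
|---|---|---|---|
| 0 | 48.6% | 75.0% | 26.4 |
| 0.2 | 53.9% | 76.8% | 22.9 |
| 0.5 | 61.5% | 80.2% | 18.7 |

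Power per endpoint with four true effects is then 91.9%, 91.2% and 90.1% under the step-down rule. The chance of finding at least one effect is unchanged (99.9% under both rules at correlation 0). In no simulated data set did the step-down rule lose a single-step rejection, and its family-wise error stayed at or below 5% at each correlation.

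**The case against.** The strongest reply is that the protocol never sets the decision rule under discussion. The level .0127 stands only in the sample-size section. A trial planning Holm-Sidak would be sized at the same .0127, because that is its first step. The Analyses section defers to outside papers, and a statistical analysis plan may exist. This stands in part. A reader might infer that .0127 is fixed for every endpoint however many others succeed, but no sentence says so. What remains is that .0127 is the only multiplicity rule in the document, described as the adjustment for the co-primary endpoints, so it is the level an analyst would naturally apply.

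The second reply is that single-step Sidak is a legitimate choice. It controls the error and comes with simultaneous intervals that match its decisions, and the trial also aims at more precise effect estimates for its economic modelling. That stands as well: there is no error, and matching intervals are a real, if small, advantage. The single-step rule's lower actual error when some effects are real (1.3% against 4.2% with three) is unused allowance below a limit that both rules respect.

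The third reply concerns size. A reader might take 49% to 75% as the expected gain. It is the best case: four true effects of d = 0.20 and independent endpoints, measured on a criterion that the protocol does not set. According to the Background section, the original trial found a significant effect on smoking only. If one behaviour responds, the gain is about 0.1 point; with two, about 2 points.

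**Conclusion.** A cheap improvement, not a correction. The stated level is valid and the 80% power claim is met. If .0127 is used as the threshold for all four six-month endpoints, power per endpoint at d = 0.20 and 600 per arm is lower than it need be by about 0.1, 2.1, 4.7 or 8.4 points with one, two, three or four true effects. The step-down rule never rejects less and holds the same 5% limit.

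This rests on an inferred 5% family-wise level, normal test statistics, independence for the per-endpoint figures, and a common d = 0.20. Sidak control, in one step or step-down, needs independence or two-sided normal statistics, so the change adds no condition.

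The gain would be larger with fewer participants at six months: at an assumed 470 per arm and four true effects, about 72% against 82% per endpoint. The protocol gives no such figure. Its retention rate is for participants with any follow-up ("was able to obtain at least one follow-up data point from 76.60% of respondents"), so no six-month number can be derived from it.

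**What to change.** Leave .0127 in the sample-size calculation, where it suits either rule and is conservative for the step-down one. Add one sentence to the Analyses section or the analysis plan, before any six-month data are examined: the four co-primary p-values are ordered from smallest to largest and compared with .0127, .0170, .0253 and .05, stopping at the first that fails. Name the method (Holm-Sidak) and state the 5% family-wise level. Plain Holm (.0125, .0167, .025, .05) is an acceptable alternative.

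The sample size does not change. The one downside is that simultaneous confidence intervals will not match the step-down decisions exactly, so report 98.7% intervals (1 − .0127) beside the decisions and say that they may differ at the margin.

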### **Analyses**

Both the data and the health economic analyses will follow the same procedure as outlined in the study protocol paper for the original U@Uni trial [14] and reported in the accompanying papers [1, 5]. Thus, multivariate analysis will be conducted to assess the impact of the intervention on each of the four targeted health behaviours at six-month follow-up, controlling for age, gender, nationality and baseline scores.

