#### **Recruitment, Randomization and Allocation**

Incoming undergraduate students to the University of Sheffield ( $N \approx 5000$ ) will be sent an email one month before the start of semester 1 with information about the study and a link to the baseline questionnaire. On completion of the baseline questionnaire participants will

be randomly allocated to one of two arms using a random number generator (as part of the LifeGuide software). Participants in both arms of the trial will be sent emails with links to the follow-up questionnaires using SurveyGizmo one and six months after starting university. All participants will receive three automatic reminders to complete the questionnaires at each time point. Participants in the intervention arm will also be sent automatic email prompts to use the intervention website after initially accessing the intervention website and shortly before the start of their second semester at university. Participants will receive incentives to complete the questionnaires by being entered into £100 prize draws at each time point. Participants who complete all three questionnaires will receive a £10 gift voucher and will be entered into a further prize draw for an iPad mini.

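### The stated six-month model gives no role to the one-month values of the same outcomes, although the sample size counts students who may have only those values

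*Protocol*

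**What the plan says.** - **Analyses.** "multivariate analysis will be conducted to assess the impact of the intervention on each of the four targeted health behaviours at six-month follow-up". The covariates are age, gender, nationality and baseline scores. One-month values appear neither as outcome nor as covariate. For the remaining procedure the section points to the published protocol of the original trial.
- **Recruitment, Randomization and Allocation.** Both arms are sent "follow-up questionnaires using SurveyGizmo one and six months after starting university".
- **Table 1.** Fruit and vegetable intake, physical activity, alcohol units and smoking status are each marked at baseline, one month and six months.
- **Sample Size Calculations.** For retention, the section takes the share of respondents in the original trial with "at least one follow-up data point", which was 76.60%. For recruitment, it takes that trial's response rate of 31.34%. Applied to about 5000 invited students, these rates give 1200, or "600 per arm of the trial".

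**The concern.** The sample-size section and the analysis section describe different sets of students. The first counts anyone who answers at one month or six months. The model in the second can use only those who answer at six months, unless missing values are handled in some way that the protocol does not state. Students who answer at one month and then leave fall in the gap.

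Two things are at stake. The first is precision: a one-month value says something about the missing six-month value of the same behaviour. The second is bias: if leaving after one month depends on behaviour at one month, and does so differently in the two arms, a comparison of six-month completers is shifted, and the one-month values could remove that part of the shift.

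**Working it through.** **1. The plan's own figures.** The count is 5000 × 0.3134 = 1567 randomised (783.5 per arm), and 1567 × 0.7660 = 1200.3. The significance level is the Šidák value for four outcomes: 1 − 0.95^(1/4) = 0.01274. For d = 0.20 and 80% power, n = 2(2.492 + 0.842)²/0.20² ≈ 556 per arm. With 600 per arm, power is Φ(0.20 × √300 − 2.492) = 83.4%. The statement that 1200 is sufficient therefore holds, provided all 600 per arm have six-month data. Without credit for covariate adjustment, 556 per arm corresponds to six-month retention of 556/783.5 = 71%.

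**2. Students counted but not used.** This number is 1567 × (0.766 − R), where R is six-month retention. R is not stated; it can be at most 0.766. At R = 0.70 it is 1567 × 0.066 ≈ 103 students. At R = 0.55 it is 1567 × 0.216 ≈ 338.

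**3. Information recovered.** Assume that everyone with a six-month value also has a one-month value. Let r be the correlation between the one-month and six-month outcomes given baseline (not stated; assumed 0.3 to 0.7). With unit SD, the variance of an arm's six-month mean is (1 − r²)/n₆ + r²/600, where n₆ = 783.5 × R. The effective sample is the inverse of this. Example with R = 0.55 and r = 0.7: 0.51/431 + 0.49/600 = 0.00200, so the effective sample is 500, against 431.

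| Six-month retention | n₆ per arm | Power, six-month values only | Power with one-month values (r = 0.3 to 0.7) | Gain in effective sample |
|---|---|---|---|---|
| 76.6% | 600 | 83.4% | 83.4% | none |
| 70% | 548 | 79.4% | 79.8% to 81.4% | 0.8% to 4.4% |
| 65% | 509 | 75.8% | 76.5% to 79.5% | 1.4% to 8.0% |
| 60% | 470 | 71.7% | 72.7% to 77.4% | 2.0% to 11.9% |
| 55% | 431 | 67.1% | 68.5% to 74.9% | 2.6% to 16.0% |

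The gain runs from 79.8 − 79.4 = 0.4 points to 74.9 − 67.1 = 7.8 points. The table takes no credit for baseline adjustment.

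**4. Possible bias.** This was simulated with no true effect, a baseline correlation of 0.5 and r = 0.5. A random 76.6% have any follow-up. Among them, six-month response depends on one-month behaviour in the intervention arm only, with log-odds of 0.25 to 0.5 per SD.

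| Six-month retention | Bias among completers (SD) | As a share of d = 0.20 |
|---|---|---|
| 75% | near zero | near zero |
| 70% | 0.006 to 0.018 | 3% to 9% |
| 65% | 0.016 to 0.030 | 8% to 15% |
| 60% | 0.02 to 0.04 | 10% to 20% |

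Bringing in the one-month values removes this part of the bias. In a separate simulation with a true effect of 0.20, dependence of equal strength in both arms left the completers' estimate at 0.20.

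**The case against.** The strongest reply is that the protocol never says the one-month values are ignored, or that students without a six-month value are dropped. It defers procedure to a cited paper that is not at hand, and missing-data handling is commonly left to an analysis plan. Imputation using the one-month values would be compatible with the sentence as written. This stands. The most that can be said is that the protocol gives those values no stated role. The six-month target is also right, since it matches the primary research question.

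A reader might infer that attrition bias is present. The documents do not support this. The four modules control access to the full website, not to the follow-up questionnaires, and both arms get the same links, reminders and incentives. The protocol gives no evidence that drop-out depends on behaviour differently by arm. Nor can bias be large in this form at high retention: with 76.6% having any follow-up, 75% six-month retention leaves at most 1.6% of students with one-month data only.

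The repair is also partial. If the same arm-specific mechanism acts on students with no follow-up at all, the simulated bias at 75% retention falls only from 0.023 and 0.047 to 0.021 and 0.043 SD. At 70% it falls from 0.031 and 0.059 to 0.023 and 0.044 SD.

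A reader might also conclude that the trial is underpowered. That does not follow either, because baseline adjustment may make up the loss. With a baseline correlation of 0.5, six-month completers alone give 85.3% power at 60% retention and 81.5% at 55%.

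The mismatch between the students counted and the students used remains after all of this.

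**Conclusion.** The point holds as a mismatch with a cheap improvement available, not as an error that invalidates the analysis. The stated model takes six-month values adjusted for baseline covariates, while the sample size credits students who may have only a one-month value. Using the one-month values is worth about 0.4 to 8 power points for retention of 70% down to 55% and r from 0.3 to 0.7, and nothing if six-month retention equals the 76.6%. Protection against bias is a possible further benefit. It is negligible near 75% retention and reaches 0.02 to 0.04 SD at 60%, but only if drop-out depends on one-month behaviour in one arm and not the other. All retention and correlation values here are assumptions, because the protocol states none.

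**What to change.** Revise the sentence in Analyses so that the primary analysis includes everyone whom the sample size counts:

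- For each of fruit and vegetable intake, physical activity and alcohol units, fit a repeated-measures model to all students with at least one follow-up value, with arm by time and baseline by time terms plus age, gender and nationality.
- For smoking status, use a repeated-measures logistic model, or multiple imputation that includes the one-month value.
- Keep the six-month arm contrast as the primary estimate.
- Report the six-month completers' analysis as a sensitivity analysis.

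If the cited procedure already brings in the one-month values, one sentence saying so would settle the point.

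The cost is a revised sentence and a little more analysis work, with no new data or contacts. The downside is reliance on drop-out being explained by the observed data. The 23.4% (100 − 76.6) expected to have no follow-up lie outside what the one-month values can correct.
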